3.0 STUDY OBJECTIVES

3.1 **Primary Objectives**

The primary objectives are:

- To evaluate the safety, tolerability, pharmacokinetics, and pharmacodynamics of bempegaldesleukin/SOC compared with placebo/SOC in patients with mild COVID-19.
- To evaluate the safety and tolerability of bempegaldesleukin administered as single IV dose and to define the RP2D of bempegaldesleukin in patients with mild COVID-19.
- To assess the effect of bempegaldesleukin on the time course and extent of changes in absolute lymphocyte counts.

3.2 Secondary Objectives

The secondary objectives listed below involve comparison of bempegaldesleukin/SOC versus placebo/SOC in patients with mild COVID-19:

- To estimate the incidence of AEs.
- To evaluate the frequency of serious AEs (SAEs).
- To determine the percentage of patients who require supplemental oxygen.
- To evaluate clinical status based on the World Health Organization (WHO) Clinical Progression Scale. This will be determined once more information is obtained about the clinical meaning/interpretation. The scale is as follows:

Patient state	Descriptor	
Uninfected	Uninfected; no viral RNA detected	
Ambulatory mild	Asymptomatic; viral RNA detected	
disease	Symptomatic; independent	2
	Symptomatic; assistance needed	3
Hospitalized:	Hospitalized, no oxygen therapy ^a	
Moderate disease	Hospitalized; oxygen by mask or nasal prongs	5
Hospitalized:	Hospitalized; oxygen by non-invasive ventilation or high-flow	6
Severe disease	Intubation and mechanical ventilation, $PaO_2/FiO_2 \ge 150$ or $SpO_2/FiO_2 \ge 200$	7
	Mechanical ventilation, $PaO_2/FiO_2 < 150$ (SpO ₂ /FiO ₂ < 200) or vasopressors	
	Mechanical ventilation, $PaO_2/FiO_2 < 150$ and vasopressors, dialysis, or ECMO	9
Dead	Death	10

Abbreviations: ECMO = extracorporeal membrane oxygenation; FiO_2 = fraction of inspired oxygen; PaO_2 = partial pressure of arterial oxygen; SpO_2 = oxygen saturation

a. If hospitalized for isolation only, record status as for ambulatory patient. Source: WHO 2020

• To assess the immunologic effects in blood before and after study drug administration, including effects on cytokines, natural killer cells, T-cells, and other serum proteins and immune modulators.

4.0 SELECTION OF STUDY POPULATION

4.1 Inclusion Criteria

Each patient will be entered into this study only if he/she meets all the following criteria:

- 1. Patient (or legally authorized representative) provides written, informed consent to participate in the study and follow the study procedures. The Investigator takes responsibility for ensuring that all vulnerable patients are protected and participate voluntarily in an environment free from coercion or undue influence.
- 2. Male or female patients, age 18 years or older on the day of signing the informed consent form (ICF).
- 3. Agrees to admission to an in-patient facility for monitoring from Days 1 to 8, inclusive.
- 4. Symptoms of mild illness with COVID-19 (eg, fever, cough, sore throat, malaise, headache, muscle pain, gastrointestinal symptoms) without shortness of breath, dyspnea, or clinical signs indicative of more serious COVID-19.
- 5. Confirmed COVID-19 determined by a positive, documented SARS-CoV-2 infection determined by a commercial or public health assay in any specimen within 4 days prior to the screening visit or during the 7-day screening period.
- 6. Respiratory rate < 20 breaths per minute.
- 7. Heart rate < 90 bpm.
- 8. Oxygen saturation by pulse oximetry > 93% on room air.
- 9. Body mass index $< 35 \text{ kg/m}^2$.
- 10. Demonstrated adequate organ function, as defined below:
 - a. Absolute neutrophil count (ANC) $\geq 1500/\mu L$ ($\geq 1000/\mu L$ for patients with known or suspected diagnosis of benign ethnic neutropenia)
 - b. Platelet count $\geq 100 \times 10^3/\mu L$
 - c. Hemoglobin $\ge 12.0 \text{ g/dL}$
 - d. Estimated glomerular filtration rate (eGFR) \ge 30 mL/min, where eGFR is estimated by the Modification of Diet Renal Disease (MDRD) equation: eGFR (mL/min/1.73 m²) = 175 × (serum creatinine)^{-1.154} × (age)^{-0.203} × (0.742 if female) × (1.212 if black)
 - e. Alanine transaminase (ALT) or aspartate transaminase (AST) or < 2 × upper limit of normal (ULN)
 - f. Total bilirubin $< 1.5 \times$ ULN

- 11. Reproductive Status
 - a. Women of childbearing potential (WOCBP) must have a negative serum or urine pregnancy test (minimum sensitivity 25 IU/L or equivalent units of human chorionic gonadotropin [HCG]) within the 7 days prior to enrollment.
 - b. Women must not be breastfeeding.
 - c. Women of childbearing potential must agree to follow instructions for method(s) of contraception for the duration of study participation or 2 weeks after the last dose of study drug, whichever is longer. Women should use an adequate method(s) of contraception as indicated in Appendix 2.
 - d. Men who are sexually active with WOCBP must agree to follow instructions for method(s) of contraception (Appendix 2) for the duration of study participation or 2 weeks after the last dose of study drug, whichever is longer. In addition, male patients must refrain from sperm donation during this time.
 - e. Investigators shall counsel WOCBP, and male patients who are sexually active with WOCBP, on the importance of pregnancy prevention and the implications of an unexpected pregnancy. Investigators shall advise on the use of highly effective methods of contraception (Appendix 2), which have a failure rate of < 1% when used consistently and correctly.
- 12. Patients must be able and willing to comply with the study procedures.
- 13. Agrees to not participate in another clinical trial for the treatment of COVID-19 while on study unless the patient's condition has worsened and is considered to be moderate, severe, or critical by the Investigator.

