	• Symptoms of mild illness with COVID-19 (eg, fever, cough, sore throat, malaise, headache, muscle pain, gastrointestinal symptoms) without shortness of breath, dyspnea, or clinical signs indicative of more serious COVID-19.
	• Confirmed COVID-19 determined by a positive, documented SARS-CoV-2 infection determined by a commercial or public health assay in any specimen within 4 days priot to the screening visit or during the 7-day screening period.
	• Respiratory rate < 20 breaths per minute, heart rate < 90 beats per minute (bpm).
	• Oxygen saturation by pulse oximetry > 93% on room air.
	• Body mass index $< 35 \text{ kg/m}^2$.
	• Estimated glomerular filtration rate (eGFR) \geq 30 mL/min.
	• Alanine transaminase (ALT) or aspartate transaminase (AST) < 2 × upper limit of normal (ULN) and total bilirubin < 1.5 × ULN.
	• Agrees to not participate in another clinical trial for the treatment of COVID-19 while on study unless the patient's condition has worsened and is considered to be moderate severe, or critical by the Investigator.
	Key Exclusion Criteria:
	• Shortness of breath, hypoxia (ie, the ratio of the partial pressure of arterial oxygen to the fraction of inspired oxygen [PaO ₂ /FiO ₂] ≤ 300 mm Hg), or signs of serious lower airway disease.
	• C-reactive protein, lactate dehydrogenase (LDH), or interleukin-6 (IL-6) > 1.5 × ULN
	• D-dimer or ferritin $> 1.5 \times ULN$.
	• Imminently requiring, or currently on, mechanical ventilation or extracorporeal membrane oxygenation (ECMO).
	• Systolic blood pressure < 90 mm Hg or diastolic blood pressure < 60 mm Hg.
	• Evidence of acute respiratory distress syndrome (ARDS) or systemic inflammatory response syndrome (SIRS)/shock.
	• Known cardiovascular history, including unstable or deteriorating cardiac disease.
	• Autoimmune disease.
	• History of pulmonary embolism (PE), deep vein thrombosis (DVT), or prior clinically significant venous or non-cerebrovascular accident/transient ischemic attack arterial thromboembolic event.
	• Central nervous system disease or evidence of central nervous system dysfunction.
	History of pulmonary disease, including cystic fibrosis.
	• Requirement for > 2 anti-hypertensive medications.
	• Unwilling to refrain from alcohol consumption from Day 1 of admission to the in-patient facility until discharge from the facility.
	• Adrenal insufficiency.

Product Dose and	Test Product: The starting dose of bempegaldesleukin will be 0.00075 mg/kg IV.

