5.6 Monitoring and Management Algorithms

5.6.1 Monitoring and Management of Elevated Hepatic Transaminases

Elevated hepatic transaminases can occur with bempegaldesleukin. The elevations in hepatic transaminases associated with bempegaldesleukin typically occur at the time of peak active cytokine concentration in the blood (Days 2-4), and are often accompanied by other AEs such as flu-like symptoms, rash, or pruritus. The transient elevations in hepatic transaminases are usually mild or moderate in severity, are not associated with increased total bilirubin, and resolve spontaneously without treatment.

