7.10 Potential Drug-Induced Liver Injury

Wherever possible, timely confirmation of initial liver-related laboratory abnormalities should occur prior to the reporting of a potential drug-induced liver injury (DILI) event. All occurrences of potential DILIs, meeting the defined criteria, must be reported as SAEs (see Section 7.7 for reporting details). A potential DILI is defined as:

• Treatment-emergent ALT or AST > 3 times ULN.

AND

• Total bilirubin > 2 times ULN or clinical jaundice, without initial findings of cholestasis (eg, elevated serum alkaline phosphatase > 2 times ULN).

AND

• No other immediately apparent possible causes of elevated liver enzymes and hyperbilirubinemia, including, but not limited to, viral hepatitis, pre-existing chronic or acute liver disease, or the administration of other drug(s) known to be hepatotoxic.

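### Inclusion criterion 10e, read literally, caps only one of the two transaminases: with ALT or AST below 2 × ULN, the other enzyme may be at any level

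*Protocol*

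**What the plan says.** Section 4.1 opens with the rule that governs the list: "Each patient will be entered into this study only if he/she meets all the following criteria". Item 10 covers adequate organ function, and its part e reads "Alanine transaminase (ALT) or aspartate transaminase (AST) or < 2 × upper limit of normal (ULN". Its opening words, "Alanine transaminase (ALT) or aspartate transaminase (AST) or", end in a second *or*, just before the inequality sign, that has nothing to join.

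The synopsis gives the same rule without the stray word: "Alanine transaminase (ALT) or aspartate transaminase (AST) < 2 × upper limit of normal (ULN) and total bilirubin < 1.5 × ULN". That sentence uses *or* between the two enzymes and *and* before bilirubin.

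Elsewhere, Section 5.6.1 says "Elevated hepatic transaminases can occur with bempegaldesleukin" and places the rises typically on Days 2 to 4. Section 7.10 begins its definition of potential drug-induced liver injury with "Treatment-emergent ALT or AST > 3 times ULN" and adds two further conditions. The SAP does not restate eligibility.

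**The concern.** The same conjunction has opposite effects on the two sides of a limit. In a rule that flags high values, *or* is strict: any one high value triggers it. Section 7.10 works this way, as do exclusion criteria 2 and 3 (CRP, LDH, IL-6, D-dimer, ferritin). In a rule that requires low values, *or* is lenient: one low value satisfies it. Item 10e is of the second kind but is worded like the first.

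The rule is binding at up to 10 sites, in the first trial of this drug in COVID-19, and the protocol says the drug can raise these enzymes. Section 5.2.1 also bars a site from falling back on an earlier laboratory result when a repeat is exclusionary, so each site has to know which transaminase values exclude. At stake are a consistent entry standard and a clean baseline against which on-study transaminase changes can be judged.

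**Working it through.** **Inputs.** The transaminase limit (Section 4.1 item 10e; synopsis), the other entry criteria (Sections 4.1 and 4.2), the liver-injury definition (Section 7.10), the DLT definition (Section 5.3.2.1.1), the escalation rule (Section 5.3.1) and the pause rule (Section 5.4). No sample-size, power or alpha figure is involved, and the plan gives no figure to reproduce.

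**Step 1: the condition as written against the both-enzymes reading.**

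| ALT | AST | As written: ALT < 2 × ULN or AST < 2 × ULN | Both: ALT < 2 × ULN and AST < 2 × ULN |
|---|---|---|---|
| < 2 × ULN | < 2 × ULN | pass | pass |
| < 2 × ULN | ≥ 2 × ULN | pass | fail |
| ≥ 2 × ULN | < 2 × ULN | pass | fail |
| ≥ 2 × ULN | ≥ 2 × ULN | fail | fail |

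The readings differ only in the two discordant rows. For example, ALT 6 × ULN with AST 1.5 × ULN passes as written, and so does ALT 0.8 × ULN with AST 10 × ULN. The written rule puts no upper bound on the second enzyme.

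**Step 2: does another criterion close the gap?** Item 10f limits bilirubin. Exclusions 2 and 3 limit LDH and ferritin, among others. Exclusion 20 removes known hepatitis B or C. Exclusion 26 lets the Investigator refuse a patient whose condition would raise the risk of taking part. None of these sets a limit on ALT or AST.

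**Step 3: overlap with the on-study signal.** The enzyme limb of Section 7.10 starts above 3 × ULN. Since 10e leaves one enzyme unbounded, a patient can pass it with that enzyme already above 3 × ULN at entry. The rises expected from the drug (Days 2 to 4) fall inside the DLT window of at least 7 days (Section 5.3.2.1). SAP Section 11.5 tabulates shifts from baseline to worst post-dose grade, so an abnormal starting value feeds into those tables too.

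**Step 4: effect on escalation if one such patient produced a misattributed DLT.**

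- Share of the dose group: 1/5 = 20%.
- Share of the two-DLT limit: 1/2 = 50%.
- With no other DLT in the cohort: 0 + 1 = 1 of 5, and the next higher dose is still allowed, exactly as with 0 of 5 (Section 5.3.1).
- With one other confirmed DLT: 1 + 1 = 2, so the dose is above the MTD (Section 5.3.1). If both fall within the first 5 or fewer patients on drug, the study is also paused (Section 5.4).

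**The case against.** The strongest reply is that the wording is loose but the consequences are well guarded.

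- A reader might infer that one such patient can decide escalation. The documents do not support that: 0 and 1 DLT in 5 lead to the same decision. The event must also occur in a patient on bempegaldesleukin (allocation is 1:1), be Grade 3 or higher, drug-related and clinically significant, and be confirmed by the Cohort Review Committee (Section 5.3.2.1.1).
- A reader might infer that a raised entry value would be counted as toxicity or liver injury. Section 7.1 says a pre-existing condition that does not worsen is not an adverse event. Section 7.10 also requires treatment emergence, raised bilirubin or jaundice without initial cholestasis, and no other apparent cause.
- A high baseline would be seen. Chemistry is measured at screening and again predose on Day 1, and SAP Section 11.5 reports change from baseline.
- A reader might infer that such a patient is simply eligible. The patient passes 10e only; every other criterion still applies, including exclusion 26.
- The hepatic risk looks modest. Section 5.6.1 calls the elevations transient and usually mild or moderate. Tables 4 and 5 list no related transaminase event among the 4 + 3 = 7 patients at 0.003 mg/kg, the highest planned dose, although seven is few.

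All of this stands, and it limits the size of the point. It does not repair the criterion. The safeguards act after entry, measure something else, or rest on opinion. Many sites would probably read the rule as covering both enzymes, but the *or* appears in both places, so a site reading it literally would be following the protocol.

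**Conclusion.** The point holds as a wording defect in an operative eligibility rule. Taken literally, 10e and the synopsis require only one of ALT and AST to be below 2 × ULN, and nothing else at entry caps the other. That sits badly under an item headed as evidence of adequate organ function. The likely intent is that both enzymes meet the limit, but that is an inference: neither document says so.

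The consequence is harder attribution of on-study transaminase changes in any patient admitted with one high enzyme. A misattributed DLT in such a patient would be 20% of a five-patient dose group and half the two-DLT limit, and would alter a dose decision only alongside a second confirmed DLT. The documents give no frequency for patients with one enzyme below and one at or above the limit, so the number affected cannot be estimated. The stray second *or* is in 10e only; the synopsis does not have it.

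**What to change.** Reword Section 4.1 item 10e and the matching synopsis line so that the existing limit, with its threshold unchanged, applies to both ALT and AST. Delete the second *or* in 10e, first confirming that no term was dropped there. If the sponsor does mean that one enzyme suffices, both places should say so outright and give the reason.

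The cost is a few words in two places. Appendix 1A already lists both enzymes for local testing, so no new assessment is needed. The downside is that patients with discordant enzymes would no longer qualify; the documents do not show how many that would be.

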4.2 Exclusion Criteria

A patient will be excluded from this study if he/she meets any of the following criteria:

- 1. Shortness of breath, hypoxia (defined as the ratio of the partial pressure of arterial oxygen to the fraction of inspired oxygen $[PaO_2/FiO_2] \le 300 \text{ mm Hg}$), or signs of serious lower airway disease.
- 2. C-reactive protein, lactate dehydrogenase (LDH), or IL- $6 > 1.5 \times ULN$.
- 3. D-dimer or ferritin $> 1.5 \times ULN$.
- 4. Imminently requiring, or currently on, mechanical ventilation or extracorporeal membrane oxygenation (ECMO) for respiratory support for COVID-19.

- 5. Systolic blood pressure < 90 mm Hg or diastolic blood pressure < 60 mm Hg.
- 6. Patients with any evidence of acute respiratory distress syndrome (ARDS) or systemic inflammatory response syndrome (SIRS)/shock.
- 7. Known cardiovascular history including unstable or deteriorating cardiac disease including but not limited to the following:
 - a. Unstable angina or myocardial infarction.
 - b. Transient ischemic attack (TIA)/Cerebrovascular accident (CVA).
 - c. Congestive heart failure (CHF) (any New York Heart Association [NYHA] Class).
 - d. Uncontrolled clinically significant arrhythmias.
- 8. Patients with a history of autoimmune disease.
- 9. History of pulmonary embolism (PE), deep vein thrombosis (DVT), or prior clinically significant venous or non-CVA/TIA arterial thromboembolic event.
- 10. Patients with central nervous system disease or evidence of central nervous system dysfunction.
- 11. Patients with any history of pulmonary disease, including cystic fibrosis.
- 12. Patients with a history of sickle cell disease.
- 13. Patients with a history of type 2 diabetes mellitus.
- 14. Patients with organ allografts.
- 15. Requirement for > 2 anti-hypertensive medications for management of hypertension (including diuretics). Patients with hypertension must be on a stable anti-hypertensive regimen for the 14 days prior to enrollment.
 Note: An antihypertensive medication that contains 2 drugs under one formulation is counted as 2 antihypertensive medications (eg, angiotensin-converting-enzyme [ACE] inhibitor plus diuretic, calcium channel blocker plus ACE inhibitor).
- 16. Use of an investigational agent or an investigational device within 28 days of enrollment and throughout the course study, except if the patient's condition has worsened to moderate, severe, or critical per the Investigator.
- 17. Female patients who are pregnant or lactating, who plan to get pregnant, or who have a positive serum or urine pregnancy test.

- 18. History of allergy to bempegaldesleukin or its components, sodium citrate and trehalose dihydrate.
- 19. Patients on chronic immune-suppressive agents (use of 10 mg/day or less of prednisone or equivalent is allowed).
- 20. Has known hepatitis B virus (HBV) infection (eg, hepatitis B surface antigen [HbsAg] reactive) or hepatitis C virus (HCV) infection (eg, HCV ribonucleic acid [RNA] qualitative is detected).
- 21. Has known immunodeficiency or active human immunodeficiency virus (HIV-1 and HIV-2 antibodies).
- 22. Prolonged Fridericia's corrected QT interval (QTcF) > 500ms.
- 23. Unwilling to refrain from alcohol consumption from Day 1 of admission to the in-patient facility until discharge from the facility.
- 24. Patients with adrenal insufficiency.
- 25. Anticipated transfer to another hospital which is not a study site within the study duration.
- 26. Any condition including medical, emotional, psychiatric, or logistical that, in the opinion of the Investigator, would preclude the patient from adhering to the protocol or would increase the risk associated with study participation or study drug administration or interfere with the interpretation of safety results (eg, a condition associated with diarrhea or acute diverticulitis).

5.0 INVESTIGATIONAL PLAN

5.1 Study Design

This study is a multicenter, Phase 1b, randomized, double-blind, placebo-controlled trial to assess the safety, tolerability, pharmacokinetics, and pharmacodynamics of bempegaldesleukin/SOC in adults with mild COVID-19, as well as to determine the RP2D of bempegaldesleukin.

5.2 Screening Period

Patients will provide written informed consent to participate in the study before completing any protocol-specified procedures or evaluations not considered to be part of the patient's standard care. After signing the ICF, patients will be evaluated for entry criteria during the up to 7-day Screening period based on assessments outlined in Section 1.2. Rescreening after screen failure may be allowed after discussion with the Medical Monitor.

5.2.1 Screening Failure

Screen failures are defined as patients who consent to participate in the clinical study but are not subsequently enrolled. A minimal set of screen failure information is required to ensure transparent reporting of screen failure patients, to meet the Consolidated Standards of Reporting Trials (CONSORT) publishing requirements, as applicable, and to respond to queries from regulatory authorities.

Patient re-screening: this study permits the re-screening of a patient who has discontinued the study as a pre-treatment screen failure (ie, patient has not been enrolled). If re-screened, the patient must be re-consented.

Retesting of laboratory parameters and/or other assessments included in the Schedule of Events (Section 1.2) within any single Screening period will be permitted if the Investigator deems the assessment does not accurately represent the patient's clinical status.

If laboratory parameters or other assessments were tested more than once, only the most current results obtained prior to enrollment will be used for assessment of eligibility. Results from earlier laboratory testing may not be substituted if repeat laboratory testing yields an exclusionary value.

5.3 Dose Finding

Dose finding is described in Table 8 and will follow the rules described in Section 5.3.1.

The first bempegaldesleukin dose to be studied (0.00075 mg/kg) was determined in consideration of a monotherapy trial with bempegaldesleukin in the oncology setting (ie, 0.003 mg/kg q3w; see Section 2.2.4.1) as well as non-clinical toxicology data (see Section 2.2.4.2) and clinical pharmacology and pharmacodynamic data (see Section 2.2.4.3, respectively). The starting dose is 12 times lower than the MTD for bempegaldesleukin

monotherapy established in patients with late-stage cancer. This dose has the potential to be pharmacologically active with a low risk of inducing hyperinflammation or toxicity in patients enrolled in Study 20-214-34 (Section 2.2.4).

	Bempegaldesleukin		
Cohort	Dose	Schedule	
-1ª	0.000375 mg/kg	single dose on Day 1	
1	0.00075 mg/kg	single dose on Day 1	
2 ^a	0.0015 mg/kg	single dose on Day 1	
3ª	0.003 mg/kg	single dose on Day 1	

Table 8:Dose Finding Scheme

a. Doses which may be chosen based on patient **response** to initial 0.00075 mg/kg dose.

In each dose cohort, the first two patients randomized and treated (1 with

bempegaldesleukin/SOC and 1 with placebo/SOC) will serve as sentinel patients. Enrollment in each cohort will be staggered as presented in Figure 2 and Table 9. The Cohort Review Committee (CRC; see Section 7.16) will monitor blinded safety and tolerability data for the first 72 hours after study drug administration from the 2 sentinel patients before additional patients in that cohort are treated. If the CRC determines additional patients may be randomized, 2 patients will be randomized (1 with bempegaldesleukin/SOC and 1 with placebo/SOC), treated with study drug, and observed for 72 hours. For every 2 patients, the Medical Monitor will review the blinded safety and tolerability data from the first 72 hours after study drug administration to determine if the next 2 patients may be randomized (see Section 5.15). If it is not possible to assess the protocol-defined DLT criteria (see Section 5.3.2.1.1), the Medical Monitor will request a review of the safety data by the CRC. After 10 patients have completed a 7-day observation period for DLT (see Section 5.3.2.1 for additional details), the CRC will determine whether dose escalation or de-escalation from the tested bempegaldesleukin dose level can proceed. The CRC will document this decision that will be based on blinded data using predefined criteria, including the proportion of patients who experience a DLT (see Section 5.3.2). Patients who drop out of the study for reasons other than a DLT, before the DLT evaluation period (Days 1 to 7) has elapsed, may be replaced.

Table 9:	Staggered Dosing	Procedures for	Each Dose Cohort

Patient	Procedure
Patients 1 and 2	Randomize Patients 1 and 2.
	CRC reviews blinded safety and tolerability data for the first 72 hours after study drug administration to determine if Patients 3 and 4 can be randomized.
Patients 3 and 4	Randomize Patients 3 and 4 if CRC approves.
	Medical Monitor reviews blinded safety and tolerability data for the first 72 hours after study drug administration to determine if Patients 5 and 6 can be randomized. ^a
Patients 5 and 6	Randomize Patients 5 and 6 if Medical Monitor approves.
	Medical Monitor reviews blinded safety and tolerability data for the first 72 hours after study drug administration to determine if Patients 7 and 8 can be randomized. ^a
Patients 7 and 8	Randomize Patients 7 and 8 if Medical Monitor approves.
	Medical Monitor reviews blinded safety and tolerability data for the first 72 hours after study drug administration to determine if Patients 9 and 10 can be randomized. ^a
Patients 9 and 10	Randomize Patients 9 and 10 if Medical Monitor approves.
	After 10 patients receive study drug and a 7-day observation period has elapsed, CRC review to determine if dose escalation or de-escalation from the tested bempegaldesleukin dose level can proceed.

a. If it is not possible to assess the protocol-defined DLT criteria (see Section 5.3.2.1.1), the Medical Monitor will request a review of the safety data by the CRC.

The CRC will decide the following:

- Continued dosing of additional patients after the first 2 sentinel patients in a new cohort are treated and a 72-hour safety review period has elapsed. If it is not possible to assess the protocol-defined DLT criteria (see Section 5.3.2.1.1), the CRC may review unblinded data in accordance with Nektar Therapeutics internal procedures for unblinding.
- If reports of Grade 3 dose-limiting toxicities meet the protocol-defined criteria for a DLT and demonstrate evidence indicating at least a possible relationship to study drug in patients confirmed to have received bempegaldesleukin. If it is not possible to assess the protocol-defined DLT criteria (see Section 5.3.2.1.1), the CRC may review unblinded data in accordance with Nektar Therapeutics internal procedures for unblinding.
- Whether dose escalation or de-escalation from the tested bempegaldesleukin dose level can proceed after 10 patients are treated in a dose cohort and a 7-day observation period has elapsed. The CRC decision will be based on the accumulated, blinded safety and tolerability data, as well as any available pharmacokinetic, pharmacodynamic, and disease measurement data. If it is not possible to assess the protocol-defined DLT criteria (see Section 5.3.2.1.1) for the entire cohort to determine dose escalation, the CRC may review unblinded data in accordance with Nektar Therapeutics internal procedures for unblinding.

- The RP2D of bempegaldesleukin based on the totality of the blinded, safety, tolerability, pharmacokinetic, pharmacodynamic, and disease measurement data. The RP2D may be determined based on the MTD dose or a dose lower than MTD. The RP2D may also be determined based on the immunologic effects of the study drugs, which could include effects on lymphocyte counts, cytokines, natural killer cells, T-cells, and other serum proteins and immune modulators. If it is not possible to assess the protocol-defined DLT criteria (see Section 5.3.2.1.1) for the entire cohort to determine dose escalation, the CRC may review unblinded data in accordance with Nektar Therapeutics internal procedures for unblinding.
- Whether dose levels other than those shown in Table 8 should be evaluated in consideration of the severity, duration, frequency of toxicities, pharmacokinetics, and/or pharmacodynamics observed at any dose.

